Heart rate	Number of heartbeats measured at minute 0, from minute 0 to 30 minutes after the procedure continuously and 30 minutes after the intervention.	Quantitative – Discrete	Beats per minute (bpm)
Respiratory rate	Number of breaths measured at minute 0, from minute 0 to 30 minutes after the intervention continuously and at 30 minutes after the intervention.	Quantitative – Discrete	Breaths Per Minute (rpm)
Oxygen saturation	Measurement of the percentage of oxygen availability in the blood, measured at minute 0, from minute 0 to 30 minutes after the intervention continuously and at 30 minutes after the intervention.	Quantitative – Discrete	Percentage of SaO ₂ (SaO ₂ %)

Description of interventions

Music therapy is a non-pharmacological therapeutic intervention that will be implemented through two modalities: live and pre-recorded music. Group A will be comprised of patients who have been exposed to live music, which will be carried out by a music therapist using the guitar as the only musical instrument. Instrumental lullabies will be used, which will be selected by the patients' legal guardians. Group B corresponds to patients who will be exposed to pre-recorded music, of the genre of lullabies, instrumental type, using a speaker that will be placed inside the patient's incubator. Group C will be those patients in whom no musical intervention will be performed.

The patient will be placed in an incubator, monitored with a vital sign monitor and pulse oximetry, and under the supervision of a research assistant. The research assistant will be responsible for recording the variables at minute 0, from minute 0 to minute 10, and 30 minutes after the completion of music therapy or non-intervention. The volume will be controlled in the three groups by means of a decibel regulator, with a maximum volume of 70 dB.

During the intervention and for a period of 30 minutes following its conclusion, singing will be prohibited by the music therapist or, in the case of groups A and B, by the parents. This prohibition will be implemented in the same manner in group C, which will be devoid of any form of music exposure in order to prevent the introduction of confounding variables. Both live and pre-recorded music will be instrumental in nature, lacking any lyrics. In accordance with the protocol for admission to the neonatal unit, the use of electronic devices is restricted. Consequently, patients will not be exposed to auditory stimuli of this nature.

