Sources of information

The source of information will be primary. Demographic and clinical data will be obtained from the medical record. The vital signs data such as heart rate, respiratory rate and oxygen saturation will be obtained from the records of the monitors of the intensive care units, at the established times, which are: at minute 0, from minute 0 to minute 10 continuously and at 30 minutes after the intervention.

Standardization of measurements

For the standardization of measurements of the different physiological variables, several elements will be considered. First, the trademark of the medical equipment manufacturer of each of the tools that will be used (vital sign monitor and pulse oximeter) will be verified, verifying that they correspond to the same commercial brand since they are different brands, there may be variability between the standard calibration measurements considered within the critical range. Second, it will be verified that each medical tool used has been calibrated in the last 6 months, recording the date of last calibration so that the device can be used during the study.

Subsequently, the professional in charge of the music company will verify that the guitar to be used during the live music is in tune and suitable for use. A decibel regulator will be used during the implementation of the pre-recorded and live music, which will adjust the volume of the sound emitted. to ensure the same decibels per research subject, with a maximum allowable of 70 dB. Vital variables will be recorded at minute 0, from minute 0 to minute 10 and at 30 minutes after the intervention.

Primary Outcome

The primary outcome of this study is the heart rate (HR), which will be measured through pulse oximetry every minute, beginning at minute 0 (prior to the intervention), then from minute 0 to minute 30 (during the intervention), and finally at 30 minutes after the intervention.

Secondary Outcomes

- Respiratory rate (RR) will be measured through pulse oximetry every minute, beginning at minute 0 (prior to the intervention), then from minute 0 to minute 30 (during the intervention), and finally at 30 minutes after the intervention.
- Oxygen saturation (SO) will be measured through pulse oximetry every minute, beginning at minute 0 (prior to the intervention), then from minute 0 to minute 30 (during the intervention), and finally at 30 minutes after the intervention.

Analysis of information

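### The protocol gives two incompatible recording windows for heart rate, the primary outcome: minutes 0–10 in the data-capture text and minutes 0–30 in the outcome definitions

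*Protocol*

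**What the plan says.** Three places in the protocol tell staff what to collect, and they agree with one another:

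- **Description of interventions** (research assistant's duty): "recording the variables at minute 0, from minute 0 to minute 10, and 30 minutes after the completion of music therapy or non-intervention".
- **Sources of information** (what is taken from the monitor records): "at the established times, which are: at minute 0, from minute 0 to minute 10 continuously and at 30 minutes after the intervention".
- Likewise under **Standardization of measurements**: "Vital variables will be recorded at minute 0, from minute 0 to minute 10 and at 30 minutes after the intervention".

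Three other places define the outcomes, and they also agree with one another, but on a different window:

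- **Primary Outcome** (heart rate): "which will be measured through pulse oximetry every minute, beginning at minute 0 (prior to the intervention), then from minute 0 to minute 30", with that stretch labelled as the intervention period: "then from minute 0 to minute 30 (during the intervention), and finally at 30 minutes after the intervention".
- For the other two vital signs, **Secondary Outcomes** has "Respiratory rate (RR) will be measured through pulse oximetry every minute" and "Oxygen saturation (SO) will be measured through pulse oximetry every minute", each on the same 0–30 schedule with one follow-up reading.

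The **Variable Matrix** has a third wording for heart rate: "Number of heartbeats measured at minute 0, from minute 0 to 30 minutes after the procedure continuously and 30 minutes after the intervention". Its rows for respiratory rate and oxygen saturation are worded almost identically.

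The description of groups A, B and C gives no session length. Ethical Considerations says the legal representative will be told how long each session lasts, but only the outcome definitions imply a figure.

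**The concern.** The text that staff work from and the text that defines the primary outcome ask for different data. Each version appears three times, so a single slip of the pen is an unlikely explanation, and no sentence gives one version precedence.

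If the data-capture text is followed, heart rate is not collected as defined. The part left out is the last two thirds of what the outcome definition calls the intervention period. Analysis of information tests the effect of music on vital signs by repeated-measures ANOVA or the Friedman test, so the recorded times determine what the within-infant factor can contain. Two teams working from this document could build different primary datasets. With both windows in the protocol, the reported one could also be chosen after the data are seen. A statistical analysis plan cannot repair this, because it cannot restore readings that were never taken.

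The follow-up reading has a related weakness. It is tied to the end of the session, whose length is not stated where the intervention is described. In group C no music ends, so its clock time is not explicit. A control reading taken at a different elapsed time would disturb the between-group comparison at that point.

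**Working it through.** The protocol states no total number of readings, so there is no figure of its own to reproduce. The check compares the windows and counts time points.

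**Inputs**

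- Capture window: minutes 0–10 plus one follow-up (Description of interventions, Sources of information, Standardization of measurements).
- Outcome window: minutes 0–30, one reading per minute, plus one follow-up (Primary Outcome, Secondary Outcomes).
- Planned infants: 45, as 15 per group (Sample size).
- Assumption: one reading per minute in the capture window too. Sources of information asks for continuous recording there, and the other two capture texts give no frequency.

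**Readings per infant per vital sign**

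| Schedule | Count | Total |
|---|---|---|
| Outcome definitions | 31 (minutes 0 to 30) + 1 | 32 |
| Data-capture text | 11 (minutes 0 to 10) + 1 | 12 |
| Difference | minutes 11 to 30 | 20 |

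Share of the defined schedule not planned for collection: 20 / 32 = 62.5%.

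**Over the planned sample**

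- Heart rate: 20 × 45 = 900 of 32 × 45 = 1,440.
- Three vital signs: 3 × 900 = 2,700 of 3 × 1,440 = 4,320.

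**Sensitivity**

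- If the pre-intervention minute 0 is counted separately from the start of the window, the totals are 33 and 13. The difference is still 20, or 20 / 33 = 60.6%.
- Under any sampling frequency the capture window still stops 20 minutes before the outcome window (30 − 10 = 20).
- The follow-up reading does not fill the gap. It falls at minute 10 + 30 = 40 if a session lasts 10 minutes (an assumption), or at minute 30 + 30 = 60 if it lasts the 30 minutes that the outcome definitions imply. Neither lies between minutes 11 and 30.

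**Variable Matrix**

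Read loosely as 0–30, the matrix matches the outcome definitions (32 readings). Read literally, it runs to 30 minutes after the procedure. With a 30-minute session and one-minute sampling that is minutes 0 to 60, or 61 readings. The wording may simply be loose, so little weight goes on this. Either way it does not support the 0–10 window.

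**The case against.** The contradiction itself is hard to dispute. The best counter-arguments concern its consequences.

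- **The intended window is unknown.** Three texts, including the one that lists the established times, say 0–10. If that was meant, the outcome definitions are wrong and no intended reading is lost. This stands as a limit on the 62.5%, which is conditional on the outcome definitions being right. It does not remove the need to reconcile.
- **Readings are not information.** Minute-by-minute values within an infant are correlated, so 62.5% fewer readings is not 62.5% less information, and no loss of power or bias has been shown. This stands. The counts measure departure from the defined outcome and nothing more.
- **The analysis may use summaries.** Analysis of information does not say that every minute enters the model. A before, during and after summary would also fit. This stands, but the meaning of a during-session summary would still depend on which window was recorded.
- **The data may not be lost.** Values come from monitor records, which may hold minutes 11–30. That is possible, but the protocol neither plans nor confirms it.
- **Group C has a matched period.** The protocol speaks of completing the non-intervention and applies the singing ban in group C as in the other groups, so an equivalent period is evidently intended. That softens the point about group C, but its length is still not explicit.

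**Conclusion.** The concern holds and must be fixed. Current text gives two incompatible recording schedules for the primary outcome and both secondary outcomes, and nothing reconciles them. If the data-capture text is followed, minutes 11–30 of the defined outcome lie outside planned collection: 20 of 32 readings per infant per vital sign, and 900 of 1,440 heart-rate readings over 45 infants.

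The counts assume one-minute sampling in both windows and take the outcome definitions as the reference. The 20-minute gap does not depend on the sampling assumption. Confidence in the contradiction is high. Whether data would actually be lost depends on which text staff follow and on what the monitors store, and the protocol settles neither.

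**What to change.** Make the three data-capture texts and the three vital-sign rows of the Variable Matrix state the same window and frequency as the Primary and Secondary Outcomes, so that every reading the primary outcome needs is collected. The 0–30 window contains the 0–10 window, so aligning this way loses nothing if the narrower one was intended. In that case the sponsor must also correct the outcome definitions.

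State the follow-up reading as a time counted from minute 0, identical in groups A, B and C. The sponsor must reconcile the session length that the outcome definitions imply with the rest of the protocol and state it in Description of interventions. No length is proposed here.

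The cost is mainly wording, because the infants are already monitored. If 0–10 was the working intention, recording grows from 12 to 32 readings per vital sign per infant (32 / 12 ≈ 2.7 times) for the same research assistant. The sponsor should confirm that the monitor records cover the full window. The protocol is dated April 30, 2024 and the study period opens on May 1, so the correction has to reach staff at once. For any infant recorded before it does, document whether minutes 11–30 can be retrieved.

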- Management with Extracorporeal membrane oxygenation (ECMO) and/or nitric oxide.
- Temperature less than 36.5 C or greater than 37.5 C.
- Patient under pharmacological sedation or use of beta-blockers.

- Congenital heart disease, operated on or not.
- Congenital malformations.
- Surgical emergencies or recovery from a surgical procedure performed within the last 48 hours.

Sample size

The sample size was determined using the G*Power 3.1.9.7 program, with a confidence level of 95%, statistical power of 90%, mean difference in heart rate between the live music therapy group (140 bpm), prerecorded music therapy group (127 bpm), and the control group (147 bpm). A total sample size of 45 was calculated, with a ratio of 1:1:1 between groups. This equates to 15 participants in each group.

Sample Selection

Stratified random sampling will be used, with two strata according to gestational age defined as follows: stratum 1 neonates <37 weeks and stratum 2 neonates ≥37 weeks. Blocked randomization (block of size 3) will be used for each stratum and for the allocation of participants to each of the intervention and control groups (1:1:1). The allocation sequence will be generated by Microsoft Excel®.

The random assignment will be concealed through the use of opaque envelopes, which will be sealed and numbered sequentially. These envelopes will be carried out by the operational coordinator of the project. The carbon paper inside the envelope will transfer the details of the random number and the group to which it will be assigned (A, B or C). This will ensure that the envelope is not permeable to intense light. The envelopes will be sealed with tamper-evident security tape and will be opened sequentially only after the participant, meeting the eligibility criteria, has received the envelope. The envelopes will be kept in a folder that will be kept on a locked shelf within each unit, which will be in the custody of the project's operational coordinator.

Blinding

It is not possible to blind the participants or the music therapist from randomization due to the nature of the intervention.

Variable Matrix

Variable name	Operational Definition	Nature and Scale of Measurement.	Unit of measurement
Date of birth	Time in which he was born.	Quantitative – Discrete	Day/Month/Year

Sex	Biological characteristics that determine whether it is female or male.	Qualitative – Nominal – Dichotomous	1: Female 2: Male

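### Baseline heart rate is a single minute-0 reading, and the follow-up in the Primary Outcome section a single reading 30 minutes after the session, so baseline-related comparisons lose precision that a short averaging window would recover

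*Protocol*

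**What the plan says.** The Primary Outcome section of the Protocol has heart rate sampled once a minute. The baseline reading is described as "beginning at minute 0 (prior to the intervention"). For the session itself the wording is "then from minute 0 to minute 30 (during the intervention"). The follow-up is given as "and finally at 30 minutes after the intervention". The Secondary Outcomes section repeats the schedule for respiratory rate and oxygen saturation.

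The other descriptions agree on baseline but not on what follows:

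- **Description of interventions:** "The research assistant will be responsible for recording the variables at minute 0, from minute 0 to minute 10, and 30 minutes after" the end of the session. Sources of information and Standardization of measurements also use minutes 0 to 10 and a point 30 minutes after.
- **Variable Matrix:** minute 0, a continuous recording whose end can be read as 30 minutes after the procedure, and a separate 30-minute point.

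No version has a window before minute 0. The infant is on a vital sign monitor and pulse oximeter (Description of interventions), and the data come from the unit's monitor records (Sources of information). Analysis of information tests the music effect by repeated measures ANOVA or the Friedman test. It names no change score, time-point contrast or baseline-adjusted model.

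**The concern.** A single minute of heart rate mixes the infant's underlying level with short-term fluctuation. With one reading as baseline, all of that fluctuation enters any comparison that uses baseline. If follow-up is also one reading, whether an effect persists 30 minutes later is answered by one number per infant. With 15 infants per arm, precision is scarce and a noisy baseline corrects chance imbalance poorly.

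The protocol already samples every minute or continuously during the session, so a few more minutes at each end looks feasible. This cannot be left to a later analysis plan: pre-session minutes that were never captured cannot be averaged afterwards.

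**Working it through.** **1. The plan's own figure.** Sample size states "with a confidence level of 95%, statistical power of 90"%, means for the "live music therapy group (140 bpm), prerecorded music therapy group (127 bpm") "and the control group (147 bpm"), and "A total sample size of 45 was calculated, with a ratio of 1:1:1 between groups". The grand mean is (140 + 127 + 147)/3 = 138. The SD of the three means is √[(2² + 11² + 9²)/3] = √(206/3) = 8.29 bpm. No SD is stated, so N = 45 can only be back-solved. With the noncentral F for a one-way ANOVA, N = 45 gives exactly 90% power at SD 15.07 (f = 8.29/15.07 = 0.55). It is the smallest balanced total for SDs from about 14.5 to 15.07. An SD of 15 is therefore compatible with the plan, but it remains an assumption.

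**2. Assumed inputs.** One-minute SD 15 bpm, so total variance V = 225. Central case: stable share 65%, so S = 0.65 × 225 = 146.25 and within-infant variance W = 225 − 146.25 = 78.75. Minute-to-minute autocorrelation r = 0.6 (AR(1)). The protocol gives none of these. From the plan: 15 per arm, and 147 − 140 = 7 bpm for live versus control. The session mean uses the 30-minute schedule of the Primary Outcome section.

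**3. Formulas.**
- Variance of a k-minute mean: S + W·f(k), where f(k) is the average of r^|i−j| over all pairs of the k minutes. At r = 0.6, f(1) = 1, f(5) = 0.523 and f(30) = 0.125.
- Residual variance after baseline adjustment: Vo − C²/Vb, where Vb and Vo are the baseline and outcome variances and C is their covariance.
- Power: two-sided 5% noncentral t, noncentrality 7/√(2·residual/15), with 45 − 3 − 1 = 41 df.

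**4. Variances.** One-minute baseline: 225. Five-minute mean: 146.25 + 78.75 × 0.523 = 187.5. Thirty-minute session mean: 146.25 + 78.75 × 0.125 = 156.1.

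**5. Session mean, ignoring carry-over (C = S).**
- One baseline reading: 156.1 − 146.25²/225 = 61.0; power 0.67.
- Five-minute baseline: 156.1 − 146.25²/187.5 = 42.0; power 0.82.

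**6. Session mean, with carry-over.** Minute 0 adjoins the session, so their short-term noise is correlated. For one reading, the average of r¹ to r³⁰ is 0.05, so C = 146.25 + 78.75 × 0.05 = 150.2. For the five-minute mean, C = 148.1.
- One reading: 55.8; power 0.71.
- Five minutes: 39.1; power 0.85.
- Saving: 1 − 39.1/55.8 = 30%.

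**7. Value 30 minutes after** (carry-over negligible).
- One reading at each end: 225 − 146.25²/225 = 129.9; power 0.38.
- Five-minute means at both ends: 187.5 − 146.25²/187.5 = 73.4; power 0.59.
- Saving: 1 − 73.4/129.9 = 43%.

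**8. Range of variance savings** over stable share 50-80% and autocorrelation 0.3-0.8:

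| Comparison | Saving |
|---|---|
| Session mean, carry-over ignored | 11-58% |
| Session mean, carry-over included | 8-58% |
| 30 minutes after | 24-66% |

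At autocorrelation 0.9 and stable share 65%, the session-mean saving with carry-over is about 1%.

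**9. The other planned differences.** They are 140 − 127 = 13 bpm and 147 − 127 = 20 bpm. With one baseline reading, session-mean power is already 0.99 or more for both. With single readings at both ends, power for the 30-minute value is 0.86 and 0.997.

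**10. Cross-check on a plain change score.** The stable level cancels, so five-minute means multiply the SD by √f(5): 0.45 at r = 0, 0.67 at 0.5, 0.85 at 0.8 and 0.92 at 0.9. That is an 8-55% reduction in SD.

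**11. If baseline is not used at all.** Comparing the follow-up value alone, with total SD 15.07 and assumed within-infant SD 4 to 10 bpm, a five-minute mean moves the overall power at N = 45 from 0.90 to between 0.903 and 0.983 over r = 0 to 0.9.

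**The case against.** A reader might infer that the primary comparison is minute 0 against 30 minutes after and that both of its ends are noisy. The protocol does not fix that. It plans repeated measures ANOVA or Friedman without naming time points. If the minute-by-minute readings are used, minute 0 and the last reading are two of about 32 levels. The ANCOVA figures above likewise assume a model the protocol does not plan. This stands, and the point is therefore limited to comparisons that use baseline or the 30-minute value.

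A reader might also take the single follow-up reading as settled. On one reading of the variable matrix, the minutes leading up to the 30-minute point are already recorded. That stands too: the follow-up half depends on which description governs. The baseline half does not.

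Recording before minute 0 is inferred from the infant being monitored; no section states it. The remedy therefore has to ask for it explicitly.

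The 7 bpm pair is the case most favourable to the concern, since N = 45 was set on three means together. Step 9 confirms that the gain is material mainly for that pair.

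Finally, a single pre-session reading is a legitimate choice and randomisation protects the group comparison. That is correct: nothing here shows bias.

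**Conclusion.** The point holds as a loss of precision that is cheap to avoid. The baseline part is firm, because every description gives minute 0 only. The follow-up part holds under the Primary Outcome wording and is conditional on reconciling it with the variable matrix.

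The documents do not determine the size. Under the assumptions in steps 2 and 8, the saving in residual variance runs from modest to substantial, and it is close to nil for the session mean if adjacent minutes are very highly correlated. The documents do not support saying that the primary comparison is compromised, that the result would be biased, or that the trial's 90% power is lost. The change is worth making before sessions start, but it ranks below settling which recording window (0 to 10, 0 to 30, or through 30 minutes after) applies.

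**What to change.** Use one schedule in the Variable Matrix, Description of interventions, Sources of information, Standardization of measurements, and Primary and Secondary Outcomes sections, and in it:

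- Capture monitor readings for the 5 minutes before minute 0 and define baseline as their mean.
- Define the follow-up value as the mean of the 5 minutes ending 30 minutes after the session. A window centred on that point would run past the period in which the protocol prohibits singing; one ending there stays inside it.
- Apply both definitions to heart rate, respiratory rate and oxygen saturation in all three arms.
- Resolve the conflicting recording windows in the same edit.

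The cost is about 5 extra minutes of monitor capture at each end per infant, plus the wording. No extra patients or procedures are needed. One drawback is that the pre-session window may include parental singing, which the prohibition does not cover. The protocol already records singing in the 30 minutes before the session as a variable, so this can be examined.

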A descriptive analysis of the variables will be performed using absolute and relative frequencies for the qualitative variables, as well as measures of central tendency and dispersion for the quantitative variables according to their normal distribution evaluated through the Kolmogorov-Smirnov test. To compare the data between the groups, one-way ANOVA or Kruskal-Wallis and chi-square ANOVA will be used. To determine the effect of music therapy on vital signs, repeated measures ANOVA or the Friedman test, if applicable, will be used. Assumptions of normality, homoscedasticity and residual distribution will be evaluated. Post-hoc comparisons are performed to determine significant differences between groups using the Student t-test. The level of significance for statistical tests will be $p < 0.05$.

A multivariate logistic regression will be performed to evaluate the effect of music therapy on respiratory rate, heart rate and pulse oximetry, considering confounding variables such as the number of visits, parental singing prior to the intervention, admission diagnosis, gestational age, comorbidities and gender.

Ethical Considerations

This research will adhere to the ethical guidelines developed by the CIOM and the WHO, as well as the stipulations of the Declaration of Helsinki for research involving human subjects. This will ensure the respect and protection of human rights, as well as the protection of the life, health, privacy, and dignity of the study subjects (24). Furthermore, this research is founded upon the tenets of bioethics, with the objective of promoting and ensuring justice, beneficence, non-maleficence, and patient autonomy, as outlined in the Belmont report from 1979 (25). Additionally, this research will have a social and scientific value, as its findings could potentially enhance the health of subjects and transform the manner in which care is delivered through the generation of reliable and valid results derived from a clinical trial. The researchers are highly qualified for the development of this research due to their expertise in pediatric and neonatal medicine, as well as epidemiology. For the administration of the interventions, a company with a high trajectory and experience in these interventions will be hired.

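### The Kolmogorov-Smirnov test is an unreliable normality check at 15 infants per arm, and the choice it may inform, repeated measures ANOVA or Friedman, should be fixed in advance because Friedman does not compare the arms

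*Protocol*

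**What the plan says.** All the relevant text is in the protocol's Analysis of information section, apart from the sample size.

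- **Descriptive summaries.** The section promises "measures of central tendency and dispersion for the quantitative variables according to their normal distribution", and the same sentence names the normality test: "according to their normal distribution evaluated through the Kolmogorov-Smirnov test". No other normality test is named. Neither the variant (plain or Lilliefors-corrected) nor the data tested (each arm, all infants, or residuals) is given.
- **Group comparison.** "To compare the data between the groups, one-way ANOVA or Kruskal-Wallis and chi-square ANOVA will be used".
- **Effect of music therapy on vital signs.** "repeated measures ANOVA or the Friedman test, if applicable, will be used". The condition under which Friedman would apply is not stated.
- **Assumption checks.** "Assumptions of normality, homoscedasticity and residual distribution will be evaluated". No method is named.
- **Sample size section.** "A total sample size of 45 was calculated, with a ratio of 1:1:1 between groups", that is, 15 infants in each arm.

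Heart rate is the primary outcome. Respiratory rate and oxygen saturation are secondary.

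**The concern.** The Kolmogorov-Smirnov test assumes a fully specified reference distribution. If the normal curve is given the sample's own mean and SD, it is pulled towards the data and the standard critical value becomes far too large. The test then hardly ever rejects. The Lilliefors critical value restores the 5% level, but power at 15 observations stays low.

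Two things are at stake. First, variables with a long tail may be reported as mean and SD because the test passed them. Oxygen saturation is the obvious candidate, since it is a percentage and cannot exceed 100. Second, the section offers two tests for the effect on vital signs and does not say how one is chosen. If normality decides, the choice rests on a weak check, and the two tests do not answer the same question.

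**Working it through.** **Inputs.** There are 45/3 = 15 infants per arm (Sample size section), and tests are at 0.05 (Analysis of information). The protocol gives assumed heart-rate means but no SD or distribution for any vital sign, so every shape below is an assumption. It states no operating figure for the normality test, so there is nothing of its own to reproduce.

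**Step 1: the test statistic.** With z_i = (x_(i) − mean)/SD from the sample, D = max over i of [i/n − Φ(z_i), Φ(z_i) − (i − 1)/n]. At n = 15 the 5% critical value is 0.338 for the plain test and 0.219 for Lilliefors. The plain test therefore demands a departure about 1.5 times as large (0.338/0.219 = 1.54).

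**Step 2: rejection rates at n = 15.** These come from 20,000 simulated samples per shape (4,000 for Shapiro-Wilk and for the gamma(2) row).

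| Assumed shape | Plain K-S | Lilliefors | Shapiro-Wilk |
|---|---|---|---|
| Normal | 0.0% | 5.0% | 5.1% |
| Gamma(4), skew 1 | 0.1% | 14.8% | 20.6% |
| Gamma(2) | 0.4% | 25% | 38% |
| Lognormal, sigma 0.5 | 0.6% | 26.2% | 38.9% |
| Exponential | 1.8% | 45.3% | 67.9% |
| Lognormal, sigma 1 | 9.9% | 65.7% | 82.7% |
| Saturation-like: 100 − exponential (mean 3), rounded | 3.7% | 59.8% | 69.5% |
| Saturation-like: N(96, 2.5) rounded, capped at 100 | 0.1% | 15.2% | 9.9% |

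**Step 3: does the unit of testing matter?**

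- *Any of three arms rejects.* Under Lilliefors, truly normal data trigger a rejection with probability 1 − 0.95³ = 14%. For lognormal(0.5) it is 1 − (1 − 0.262)³ = 60%, and for exponential 1 − (1 − 0.453)³ = 84%. For plain K-S the simulated figures are 1.9% and 5.2% for the two skewed shapes.
- *45 pooled within-arm residuals.* Plain K-S detects 6% (lognormal 0.5) and 21% (exponential). Lilliefors detects 59% and 87%.

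Pooling helps, but the plain test remains weak for these shapes.

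**Step 4: does a missed departure damage ANOVA?** The simulated type I error of one-way ANOVA with 15 per arm is 4.6% for gamma(4), 4.6% for lognormal(0.5), 4.4% for exponential and 3.4% for lognormal(1). The nominal level is 5%, so there is no inflation.

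**Step 5: what the fallback tests.** Friedman ranks the time points within each infant and asks whether the rank sums differ between times. It has no term for arm. In simulation, Friedman pooled over arms rejected 98% of the time when all arms shared a time trend and there was no arm effect. It rejected 2% of the time when the arms had opposite trends. The percentages depend on the trend sizes assumed; the pattern follows from the construction of the test. Run separately in each arm, it gives three within-arm results and still no comparison. Repeated measures ANOVA with arm as a between-subject factor can test group-by-time.

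**The case against.** Several points on the other side stand.

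- **The switch is inferred.** A reader might take it that the protocol makes Kolmogorov-Smirnov the rule for choosing parametric or rank tests. It does not. The test is named in the sentence on descriptive summaries, and the later sentences do not mention it. Normality is the natural meaning of the alternatives offered, but if that link is denied, the choice has no stated rule at all.
- **It is not the only safeguard.** The section also commits to evaluating normality, homoscedasticity and residuals. The method of doing so could properly sit in a statistical analysis plan, which is not at hand.
- **The near-zero detection belongs to one variant.** It holds for the uncorrected test. With the Lilliefors correction, detection is low to moderate.
- **Shapiro-Wilk is not a clear cure.** It is stronger for the continuous skewed shapes. For capped, rounded, saturation-like data the advantage largely goes: three further assumed shapes gave Lilliefors/Shapiro-Wilk rejection of 24%/15%, 37%/41% and 51%/52%.
- **The loss in inference is modest.** On those three shapes, with a 2-point shift in one arm, ANOVA/Kruskal-Wallis power was 82%/79%, 89%/87% and 73%/84%. Only the last shows a material gain for ranks. Nothing in the protocol suggests that heart rate is markedly skewed.
- **The two harms belong largely to different variants.** A plain test that nearly always passes the data leaves little switching; it mainly affects the summaries. Erratic switching is the Lilliefors problem.

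It can also be said that Kruskal-Wallis, listed for comparing groups, is a between-arm rank test. That is so, but the sentence devoted to the effect on vital signs offers Friedman as the alternative, and the objection does not remove that.

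**Conclusion.** The point holds in a limited form and is worth correcting. The one normality test named is a poor choice at 15 per arm: near-zero level and under 2% power against moderate to strong skew if uncorrected (up to about 10% for the extreme lognormal(1) shape), and erratic if corrected. The protocol fixes neither the variant nor the unit. All power figures rest on assumed distributions.

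It would be wrong to conclude that the primary analysis is invalid or that false positives are inflated; the ANOVA results show otherwise. The real consequences are two. Skewed variables may be described as if normal, which the text does tie to this test. And a data-driven choice remains for the analysis of vital signs, including the primary outcome, between one method that can compare arms over time and one that cannot. The second matters more, and it stands whichever normality test is used.

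**What to change.** 1. Remove the Kolmogorov-Smirnov test as a decision rule, and do not put another normality pre-test in its place.
2. Prespecify one repeated-measures model for heart rate with group, time and group-by-time, and name the between-arm contrast of interest. Check residuals graphically; use the check to qualify the result, not to select the test.
3. Replace the Friedman alternative with a prespecified sensitivity analysis that compares arms, either rank-based or on a transformed scale. This matters most for oxygen saturation.
4. Report median and IQR alongside mean and SD for every quantitative variable, so that no test has to choose between them.

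The cost is a sentence or two of analysis text and slightly longer tables. No additional infants, measurements or visits are needed.
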